### **3.2b Secondary objectives**

- To determine the acceptability of outcome data collection to participants by measuring the completion rates of PROMs
- Assess harms associated with participation in the study
- To determine what assessment findings are consistent with a diagnosis of LPD.
- Assess delivery of the intervention

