- Harms. For this study harms will be defined as any unfavourable sign or symptom related to completing the study intervention. The recording of harms has been recommended in feasibility studies to inform future research design and processes. This will be measured from commencement of the intervention to 3 month follow-up as outlined in section 6.2a.
- Determine what assessment findings are consistent with a diagnosis of LPD. A member of the trauma and orthopaedic team will be required to assess the presence/absence of proposed assessment findings to include in the eligibility criteria for future studies as outlined in section 5.1. This will inform the feasibility of using these assessment findings in the eligibility criteria for future studies.

- Intervention delivery. Treatment logs will be analysed to record the duration from injury to commencing the intervention, the number of physiotherapy sessions received by participants, the duration of intervention and the exercises prescribed.

Additional demographic data will be collected as part of the study. Further information on this and the time points for data collection are outlined in section 5.1

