## **SECTION 5 METHODS: DATA COLLECTION, MANAGEMENT, AND ANALYSIS**

### **SECTION 5.1 Data collection methods**

#### **5.1a Outcomes and time points at which they will be assessed**

Outcome	Measurement	Time point
Demographics	Age, sex, height, weight, affected knee, mechanism of injury (traumatic/atraumatic), previous history of ipsilateral patella dislocation, previous history of contralateral patella dislocation,	Baseline

	time from injury to presentation to acute care (ED or trauma services), family history of patella dislocation, employment status, level of education, ethnicity	
Assessment findings	
Presence/absence of the following on:
 
 
• A convincing patient history of a visible deformity on the lateral aspect of the knee or a sensation of the patella ‘popping’ out of joint followed by spontaneous reduction
 
• Presence of a haemarthrosis or joint effusion on clinical examination
 
• Tenderness along the medial patellofemoral complex (tenderness at the following bony landmarks or at any point extending between these two points: at or just proximal to the medial epicondyle of the femur and the midpoint of the medial aspect of the patella extending to the junction of the medial quadriceps tendon and the patella)
 
• Apprehension on laterally directed force of the patella
 
	Baseline
Eligibility	% of participants with a diagnosis of LPD who meet the eligibility criteria	Completion of study
Recruitment	
% of eligible participants who consent to participate in the study
 
Reasons for not consenting will also attempt to be collected
	Completion of study
Adherence	% of scheduled physiotherapy sessions attended	
Completion of intervention
 
3 months post first

	Participant self-reported % of prescribed home exercise sessions completed	physiotherapy session
Acceptability	% attrition rate  Patient satisfaction questionnaire	Completion of study  3 months post first physiotherapy session
Follow up	% of participants who consent to treatment who return 3 month questionnaires	Completion of study
Knee function, pain and instability	Lysholm Knee Scoring Scale	Baseline, 3 months post first physiotherapy session
Activity level	Tegner Activity Scale	Baseline, 3 months post first physiotherapy session

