### **5.1b Baseline data collection**

All baseline data will be collected after informed consent to participate in the study has been obtained prior to the first physiotherapy session. Participants will be asked to complete a questionnaire at baseline to capture the demographic information and PROMs outlined in section 5.1a. Telephone or email contact will be used to obtain a score, where relevant, if baseline data collection is subsequently identified as being incomplete.

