## 6.2b Serious adverse events

A serious adverse event (SAE) is any untoward medical occurrence that:

- Results in death,
- Is life-threatening,
- Requires inpatient hospitalisation or prolongation of existing hospitalisation,
- Results in persistent or significant disability/incapacity, or
- Consists of a congenital anomaly or birth defect.

Other “important medical events” may also be considered serious if they jeopardise the participant or require an intervention to prevent one of the above consequences. The term “life-threatening” in the definition of “serious” refers to an event in which the participant was at risk of death at the time of the event; it does not refer to an event which hypothetically might have caused death if it were more severe.

A SAE arising due to completion of the exercise intervention during this study is unlikely. If a SAE occurs during the period from commencing to finishing the exercise intervention, a SAE form must be completed by the participant’s clinician and forwarded to *CF* or one of his academic supervisors within 24 hours. *CF* in discussion with his supervisors *SH*, *MH* and *DK* will determine if the SAE is attributable to the intervention.

Only SAEs that are:

- Related to the study (i.e. they resulted from administration of any of the research procedures) and
- Unexpected (i.e. not listed in section 6.2a as an expected occurrence)

will be reported to the Research Ethics Committee (REC) who granted the study a favourable opinion approval and the study sponsor within 15 days of *CF* or his supervisors becoming aware of the event. It will be followed up until conclusion. If it is not deemed related to the intervention it will be recorded in the case report form.

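### Section 6.2b reports SAEs caused by any research procedure, but assigns a causality decision only for the intervention and requires SAE forms only once the intervention starts

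*Combined protocol and SAP*

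**What the plan says.** **Reporting criterion (6.2b).** Only SAEs that are both unexpected and study-related go to the ethics committee and sponsor. Study-related is spelled out as "Related to the study (i.e. they resulted from administration of any of the research procedures) and". Unexpected means absent from the list in 6.2a.

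**Causality decision (6.2b).** The investigator, in discussion with the supervisors, "will determine if the SAE is attributable to the intervention". The closing sentence sends an SAE not considered related to the intervention to the case report form.

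**SAE window (6.2b).** "If a SAE occurs during the period from commencing to finishing the exercise intervention, a SAE form must be completed".

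**Harms window and scope.** Section 4.4b says of harms: "This will be measured from commencement of the intervention to 3 month follow-up". The schedule in 5.1a agrees. Sections 4.4b and 6.2a define harms and adverse events as signs or symptoms related to completing the intervention. The objective in 3.2b is broader: "Assess harms associated with participation in the study".

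**Baseline examination.** Section 4.4b requires a member of the trauma and orthopaedic team to assess whether listed findings are present. The list in 5.1a includes "Apprehension on laterally directed force of the patella", with baseline as its time point. On timing, 5.1b says: "All baseline data will be collected after informed consent to participate in the study has been obtained prior to the first physiotherapy session". Section 4.7a describes the clinic assessment by the same team as usual practice and places it before eligibility is checked and the study is offered.

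**The concern.** The question that decides whether an SAE is reported is wider than the question anyone is told to answer. Someone following 6.2b literally would ask whether the exercises caused the event, answer no, enter it in the case report form and stop. Whether another research procedure caused it is assigned to nobody.

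The window adds to this. Participation begins at consent, but the duty to complete an SAE form begins with the intervention. If the lateral-force test on a recently dislocated knee is done in between, a physical study procedure sits where there is no form.

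At stake is whether the ethics committee and sponsor would be told of a serious event caused by the study. Section 6.1 says there will be no data monitoring committee, so 6.2b is the defined escalation route. The findings are also being considered as eligibility criteria for future studies (4.4b), so a serious event from eliciting them would be useful to know about.

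**Working it through.** The plan states no figure on this point and no arithmetic applies. The check sets the rules side by side and follows an SAE through them.

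**Inputs**

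| Rule | Scope | Section |
|---|---|---|
| Reportable if related to | any research procedure | 6.2b |
| Causality decision made on | the intervention only | 6.2b |
| If not related to the intervention | case report form | 6.2b |
| SAE form required | start to finish of the intervention | 6.2b |
| Adverse events and harms | related to the intervention, counted from its start | 4.4b, 5.1a, 6.2a |
| Baseline data | after consent, before the first session | 5.1b |

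**Cases**

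1. *Onset after the intervention starts, caused by the intervention.* A form is completed, the decision is yes, and the SAE is reported if unexpected. The two tests agree.
2. *Onset after the intervention starts, caused by another research procedure.* A form is completed, because the form requirement does not depend on cause. The decision is then no, and the closing sentence sends the SAE to the case report form. It is captured but may go unreported, although it meets the stated criterion.
3. *Onset after consent and before the intervention starts.* No form is required, no causality decision is triggered, and the harms definition and window both exclude it. It has no collection route.
4. *Participant consents, is examined and never starts treatment.* As case 3, because the window never opens.

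**Is there a physical procedure in the gap?** Sections 4.4b, 5.1a and 5.1b together place the required findings after consent and before the first session. Section 4.7a allows another reading: the team examines the knee as usual, before consent, and the study only needs the result recorded. It also describes patients referred straight from the Emergency Department who are not seen in the new patient clinic, so that clinic's examination cannot be assumed for them. The sections do not settle when the test is done.

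**How long is the gap?** On the referral route, consent is arranged for the first physiotherapy appointment (4.7a), so the gap is short. On the clinic route the documents do not give the wait.

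**Would a captured SAE be reported?** Not always. Section 6.2a lists recurrent patellar dislocation as expected, though as a complication of rehabilitation, so it might fail the unexpectedness test.

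**The case against.** The strongest reply is that the harm pathway rests on an unsettled premise. If the knee is examined as usual care before consent, the lateral-force test is not a research procedure, and starting SAE collection at consent would not cover it. That stands as far as the example goes. It does not repair the mismatch between the two tests, and 5.1b as written points the other way.

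Second, the reporting rule is stated separately, has no start date, and its 15-day clock runs from awareness of the event, not from a form. A known, unexpected SAE caused by a study procedure therefore qualifies as written. This also stands: the narrower question does not override the rule. But the closing sentence gives a contrary instruction, and before the intervention starts nothing requires anyone to make the event known.

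Third, a reader might infer that the plan contradicts its own objective on harms of participation. The documents do not support this. Section 4.4b explicitly defines harms by reference to the intervention and 6.2a matches, which is a legitimate choice of scope in a study that 6.1 considers minimal risk.

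Fourth, a reader might infer that an SAE from the examination would always be lost. That is too strong. Any SAE during the intervention gets a form whatever its cause; only onset before the intervention lacks one.

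**Conclusion.** The point holds as an inconsistency within 6.2b and a late start to SAE collection. An SAE with onset between consent and the start of the intervention has no form and no assigned causality decision. An SAE with later onset gets a form but may be filed as unrelated although another research procedure caused it.

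The mismatch between the two tests depends on no assumption. That the baseline examination is one of the procedures concerned assumes it is done after consent, as 5.1b says.

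The practical size is small and cannot be quantified from the documents, which give neither a rate for such events nor the clinic-route wait. In 15 participants they are expected to be rare, and the most plausible one, a further dislocation, might not be reportable to the ethics committee even when captured. The case for changing the text is that it is a cheap safety correction, not that missed events are likely.

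**What to change.** 1. In 6.2b, change both the causality decision and the closing sentence so that they ask whether the SAE is related to any research procedure, including the intervention, and record which procedure.
2. In 6.2b, start SAE collection at signed consent.
3. Show any events before the first session on a separate line of the harms table. The intervention-related harms count, as scoped in 4.4b and 6.2a, then stays unchanged.
4. Reconcile 4.4b, 4.7a, 5.1a and 5.1b on whether the listed findings come from the usual clinic examination before consent or from an assessment after it, and say who does this for patients not seen in the new patient clinic.

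The cost is a few wording changes and one table line, with no added visits. The downside is that a few pre-treatment events unrelated to the study will be recorded.

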## **SECTION 7: ETHICS AND DISSEMINATION**

### **SECTION 7.1 Ethical approval**

UK NHS ethical approval for this protocol and associated documents will be sought from the local REC prior to enrolment of the first study participant. The study will be conducted in accordance with ethical standards which include Good Clinical Practice (GCP) and the Declaration of Helsinki.

### **SECTION 7.2 Protocol amendments**

Any amendments to the protocol after ethical approval that affect the safety of study subjects, scientific value of the study, conduct or management of the study will be classed as substantive. Decisions to implement substantive amendments to the protocol will be taken by members of the study team in conjunction with the study sponsor and communicated to the local REC and the Health Research Authority (HRA) within 3 days by means of an amendment form generated through Integrated Research Application System (IRAS). All protocol amendments will be accompanied by an appropriate amendment to the protocol version and date. If substantive amendments are made after enrolment of the first participant, these will be outlined in the final study report.

### **SECTION 7.3 Consent**

Written consent will be obtained in accordance with GCP guidelines and by a researcher identified in the delegation log as being able to take consent. Participants will be informed about the study design, aims of the study and what it will involve for them. Participants will be informed the purpose of the study is not to assess the efficacy of the intervention. Participants will also be provided with written information in the form of a participant information sheet and offered an opportunity to ask questions. Participants will be offered time to consider their participation in the study should they wish to do. Participants will be informed their participation is voluntary and ongoing, and they can withdraw consent at any time with no obligation to explain why and without affecting the quality of their care.

If participants are happy to proceed to enrolment in the study the consent form will be signed and dated by the participant and the researcher. A copy will be provided to the patient, a copy will be placed in the patient's medical notes, and the original kept by the study team.

## **SECTION 7.4 Confidentiality**

The study staff will ensure participant's anonymity is maintained. Each participant will be assigned a unique subject code/number. All study documents, except the signed consent form and contact details for postal questionnaires, will refer to the patient by their unique subject code/number only. All study documents will be stored securely in locked filing cabinets accessible by study staff and authorised personnel only. Only staff involved in running the study and responsible members from Oxford University Hospital Foundation Trust, the sponsor City, University of London, and other authorities that audit and quality assure health research the NHS will have access to this information. The study will comply with the Data Protection Act and GDPR protocols, which state all data should be anonymised as soon as it is practical to do so and stored in accordance to their guidelines.

## **SECTION 7.5 Declarations of interests**

*CF* is in receipt of a MRes Clinical Research NIHR Studentship Award and employed by Oxford University Hospital Foundation Trust as a band 6 trauma outpatient physiotherapist. Competing interests: none.

*MH* is supported by the NIHR (NIHR Programme Grants for Applied Research RPPG-1210-12011) Competing interests: none.

*SH* is supported by City, University of London and has funding for research from the Bart's Charity, NIHR RfPB scheme, and the EPSRC. Competing interests: none.

*DK* is supported by the NIHR (NIHR Post Doctoral Fellowship, [name], PDF-2016-09-056). Competing interest: none.

## **SECTION 7.6 Access to data**

*CF*, *MH*, *SH* and *DK* will have access to an anonymised version of the dataset. Direct access will be granted to authorised representatives from the Sponsor and host institution for monitoring and/or audit of the study to ensure compliance with regulations. Upon completion of the study, and with participant consent, fully anonymised research data may be shared with other organisations and researchers.

## **SECTION 7.7 Ancillary care**

Any AEs related to the study intervention will be managed as outlined in section 5.2a. Any serious adverse events will be managed by standard local NHS pathways.

## **SECTION 7.8 Dissemination policy**

### **7.8a Study results**

The study will be reported in line with the Consolidated Standards of Reporting Trials (CONSORT) guidelines for pilot and feasibility trials. The exercise intervention will be reported in line with the Template for Intervention Description and Replication (TIDieR) guidelines for reporting of interventions.

CF will initially write up the results as a dissertation for a Masters in Clinical Research at City, University of London. Following submission all authors will review and agree upon the final version to be submitted for publication to a peer reviewed academic journal. Submission for publication will be made regardless of study results. Participants will be asked if they wished to be informed of study results as part of the consenting process.

### **7.8b Authorship**

Authorship will be granted in accordance with the International Committee of Medical Journal Editors' guidelines. Contributors who do not meet these criteria will be acknowledged.

### **7.8C Reproducible research**

The study will be prospectively registered on ClinicalTrials.gov. prior to enrolment of the first participant.

